10.2 Statistical Hypotheses

The primary endpoints will be tested in a hierarchical fixed sequence in the following order.

The statistical hypotheses for the primary endpoint of change from baseline corneal fluorescein staining (NEI scale) total score at Day 29 are as follows:

 H_{01} : The difference, between study eyes treated with CyclASol and study eyes treated with vehicle, in the mean change from baseline corneal fluorescein staining (NEI scale) total score at Day 29 = 0.

 H_{A1} : The difference, between study eyes treated with CyclASol and study eyes treated with vehicle, in the mean change from baseline corneal fluorescein staining (NEI scale) total score at Day 29 \neq 0, with superiority claimed if the difference is less than 0 (CyclASol minus vehicle).

The statistical hypotheses for the primary endpoint of the change from baseline total OSDI score at Day 29 are as follows:

 H_{02} : The difference, between subjects treated with CyclASol and subjects treated with vehicle, in the mean change from baseline total OSDI score at Day 29 = 0.

 H_{A2} : The difference, between subjects treated with CyclASol and subjects treated with vehicle, in the mean change from baseline total OSDI score at Day $29 \neq 0$, with superiority claimed if the difference is less than 0 (CyclASol minus vehicle).

Hierarchical fixed sequence testing will be employed to maintain the type I error rate. The primary analyses will first test the difference in the mean change from baseline corneal fluorescein staining (NEI scale) total score between treatments at Day 29. If the test of the difference is statistically significant at the two-sided alpha = 0.05 level in favor of CyclASol, then the study will be considered a success; CyclASol will be declared to be superior to vehicle in the mean change from baseline corneal fluorescein staining (NEI scale) total score at Day 29; and the difference in the mean change from baseline total OSDI score between treatments at Day 29 will be tested at the two-sided alpha = 0.05 level.

If in addition to a statistically significant test of the difference in the mean change from baseline corneal fluorescein staining (NEI scale) total score at Day 29 in favor of CyclASol, the test of the difference in the mean change from baseline total OSDI score at Day 29 is also statistically significant in favor of CyclASol, then CyclASol will be declared to be superior to vehicle in both the mean change from baseline corneal fluorescein staining (NEI scale) total score at Day 29.

10.3 Sample Size

One-hundred forty-two (142) ITT subjects (study eyes) per treatment group yields 90% power to reject H_{01} in favor of H_{A1} and conclude superiority of CyclASol over vehicle in the mean change from baseline corneal fluorescein staining (NEI scale) total score at Day 29 assuming a true difference (CyclASol minus vehicle) of -0.85, a common standard deviation of 2.2, and a two-sided alpha = 0.05. Additionally, 142 ITT subjects per treatment group yields 82% power to reject H_{02} in favor of H_{A2} and conclude superiority of CyclASol over vehicle in the mean change from baseline total OSDI score at Day 29 assuming a true difference (CyclASol minus vehicle) of -5.0, a common standard deviation of 14.5, and a two-sided alpha = 0.05. Accounting for subject discontinuations, 316 total subjects will be enrolled

For justification of clinical relevance of selected differences see Section 6.1.4.

10.4 Statistical Analysis

10.4.1 General Considerations

The quantitative variables will be summarized using number of subjects (n), mean, median, standard deviation, minimum and maximum. The qualitative variables will be summarized using counts and percentages.

All summaries will be presented by treatment group. Summaries will be provided for demographics, baseline medical history, concurrent therapies, and subject disposition. For the purpose of summarization, medical history, concurrent therapies, and AEs will be coded to MedDRA and WHO Drug dictionaries, as appropriate.

Baseline is defined as the last non-missing measure prior to administration of study drug and change from baseline will be calculated as Visit – Baseline.

10.4.2 Unit of Analysis

Safety endpoints will be analyzed for both eyes. For efficacy endpoints, the unit of analysis will be the "study eye" as defined by the following:

10.4.3 Missing Data

The primary analysis will use the FAS with available data per subject. Additional robustness analyses will include repeating the primary analysis on the PPS; the FAS imputing missing data using LOCF; the FAS imputing missing data using Markov Chain Monte Carlo (MCMC) multiple imputation methodology under different assumptions of missingness (at random and not at random); and an analysis of trimmed means (Permutt et al., 2017).

No secondary efficacy endpoints or safety endpoints will be imputed.

10.4.4 Multiplicity Considerations

Fixed sequence testing will be employed to maintain the type I error rate. The primary analyses will first test the difference in the mean change from baseline corneal fluorescein staining (NEI scale) total score between treatments at Day 29. If the test of the difference is statistically significant at the two-sided alpha = 0.05 level in favor of CyclASol, then the study will be considered a success; CyclASol will be declared to be superior to vehicle in the mean change from baseline corneal fluorescein staining (NEI scale) total score at Day 29; and the difference in the mean change from baseline total OSDI score between treatments at Day 29 will be tested at the two-sided alpha = 0.05 level.

If in addition to a statistically significant test of the difference in the mean change from baseline corneal fluorescein staining (NEI scale) total score at Day 29 in favor of CyclASol, the test of the difference in the mean change from baseline total OSDI score at Day 29 is also statistically significant in favor of CyclASol, then CyclASol will be declared to be superior to vehicle in both the mean change from baseline corneal fluorescein staining (NEI scale) total score and the mean change from baseline total OSDI score at Day 29.

[figure not shown]
10.4.5 Primary Efficacy Analyses

The primary comparisons in this study will be between CyclASol versus vehicle at Day 29. The primary efficacy endpoints (e.g. change from baseline in corneal fluorescein staining [total NEI] and OSDI) will be analyzed separately using an ANCOVA model with terms for baseline value, treatment, and the interaction of treatment by baseline value (the interaction term will be maintained in the model only if the p-value for the term is <0.10).

Least squares mean for each treatment group and for the difference between treatment groups will be presented from the model together with two-sided p-values and 95% confidence intervals. In the event that the interaction of treatment by baseline value is significant, estimate and contrast statements will be used to determine the treatment group means and differences at the 25th, 50th, and 75th percentile of the baseline score over treatment groups.

Two-sample t-tests and Wilcoxon rank sum tests comparing treatment groups will be performed as sensitivity analyses. A mixed-effect repeated measures model will also be used as an additional sensitivity analysis of mean scores and mean changes from baseline at each visit. This model will include treatment, visit, and the interaction between treatment and visit as fixed effects, and subject as a random effect. An unstructured covariance matrix will initially be used to model the covariance among repeated measures; however, if the model fails to converge using this covariance structure, either heterogeneous TOEPLITZ, homogeneous TOEPLITZ, or CS (compound symmetry) will be implemented according to the Akaike information criterion with a correction for finite sample sizes (AICc). As an additional sensitivity analysis, a mixed-effect repeated measures model will be used with the covariance matrix selected from unstructured, heterogeneous TOEPLITZ, homogeneous TOEPLITZ and CS according to AICc.

10.4.8 Safety Variables

Adverse events (AEs) will be coded using the MedDRA dictionary. Frequencies and percentages of subjects with TEAEs, serious TEAEs, and TEAEs causing premature discontinuation will be provided by treatment group. An AE is treatment emergent if it 1) occurs after the first dose of randomized study treatment or 2) if it is present prior to receipt of randomized study treatment but worsens in severity or increases in frequency after the first dose of randomized study treatment. Furthermore, frequencies will be given of subjects with TEAEs by system organ class and preferred term; by system organ class, preferred term and maximal severity; by system organ class, preferred term and strongest relationship; by system organ class and preferred term for SAEs; and by system organ class, preferred term, and day of onset. Separate analyses will be performed for ocular specific and all AEs (including systemic).

Other safety endpoints including visual acuity, slit lamp biomicroscopy, intraocular pressure (IOP) and dilated fundoscopy, will be summarized by treatment group and visit using descriptive statistics. Changes or shifts from baseline will also be summarized where appropriate.

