Dosage/Dose Regimen:	2) Vehicle Ophthalmic Solution (F4H5)					
	A 14-day study-run-in period will be used for subject selection before randomization. During this period, all subjects will receive Systane [®] Balance to dose with bilaterally BID.					

Summary of Visit Schedule:	 This clinical study involves 6 visits over the course of approximately 14 weeks: Visit 0, Day -14 ± 2 days, Screening; Visit 1, Day 1, Baseline/Randomization; Visit 2, Day 15 ± 1 days, 2-Week Follow-Up; Visit 3, Day 29 ± 2 days, 4-Week Follow-Up; Visit 4, Day 57 ± 2 days, 8-Week Follow-Up; and Visit 5, Day 85 ± 2 days, 12-Week Follow-Up and Study Exit.
Measures Taken to Reduce Bias:	and vehicle-controlled clinical study.
Study Population Characteristics:	
Number of Subjects:	Approximately subjects will be screened to enroll at least 316 (158 per treatment arm) subjects at approximately 10 sites.
Condition/Disease:	Dry Eye Disease (keratoconjunctivitis sicca)
Condition/Disease: Inclusion Criteria:	 Dry Eye Disease (keratoconjunctivitis sicca) Each subject must: a. Be at least 18 years of age; b. Provide written informed consent; c. Have a subject reported history of Dry Eye Disease ; d. Be currently using (within 30 days before Visit 0) over-the-counter (OTC) eye drops, lubricating gels and/or artificial tears for dry eye symptoms at Visit 0; e. Have an OSDI[®] score of at Visit 0 and Visit 1; f. Have a total corneal fluorescein staining score of g. Have a total lissamine green conjunctival score (sum of temporal and nasal regions) h. Have an unanesthetized Schirmer's Test score

	participate in all study assessments and visits.
Exclusion Criteria:	Each subject must not:
	 a. Have any clinically significant slit-lamp findings at Visit 0 that require prescriptive medical treatment and/or in the opinion of the investigator may interfere with study parameters including trauma, Steven Johnson Syndrome, advanced epithelial basement membrane disease;
	 c. Have abnormal lid anatomy (e.g. incomplete eyelid closure, entropion, or ectropion) or abnormal
	e. Have an ocular or periocular malignancy;
	g. Have a history of herpetic keratitis;
	h. Have active ocular allergies or ocular allergies that may become active during the study period;
	 Be diagnosed with an ongoing ocular or systemic infection (bacterial, viral, or fungal), including a fever, or be undergoing treatment with antibiotics at Visit 0 or Visit 1;

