4 STUDY DESIGN

4.1 Overall Study Design

This is a Phase 2b/3 multicenter, randomized, double-masked, and vehicle-controlled clinical study to evaluate the efficacy, safety and tolerability of CyclASol 0.1% Ophthalmic Solution in subjects with DED. Approximately 316 subjects of either sex and of any race who are at least 18 years of age with a subject-reported history of dry eye in both eyes and meeting all other study eligibility criteria will be randomized at approximately 10 sites in the US to receive treatment with CyclASol or vehicle in a 1:1 ratio (approx. 158 subjects per treatment arm). This study is composed of two distinct parts: a 14-day run-in period and an 85-day treatment period. During the run-in period, subjects will dose Systane Balance bilaterally BID for approximately two weeks. Eligible patients will thereafter dose the study treatment (CyclASol or vehicle) bilaterally BID for approximately 3 month. A chart illustrating the study's structure is below.

	Informed consent (incl. HIPAA) Demographics, medical/medication history & ocular history
	Review of qualification criteria
Visit 0	Urine pregnancy test (as needed)
Day -14 ± 2 days	Symptom questionnaires,
Screening	Eye evaluations (Efficacy /Safety)
	AE query
	In-office dose of run-in
	Dispensation of subject diary and run-in to qualified subjects

 \downarrow

Approximate 14-Day Run-In Period with Systane Balance

\downarrow

	Collection and review of run-in/diary
	AE query, medical/medication update
	Review of qualification criteria
Visit 1	Symptom questionnaires,
Day 1	Eye evaluations (Efficacy /Safety)
Baseline / Randomization	Randomization
	In-office dose and drop comfort scale and questionnaire
	Dispensation of study drug and subject diary

 \downarrow

Visit 2 Day 15 ± 1 day 2-Week Follow-Up	Collection and review of study drug/diary AE query, medical/medication update Symptom questionnaires Eye evaluations (Efficacy /Safety) Redispensation of study drug and dispensation of subject diary
	subject diary

Visit 3	Collection and review of study drug/diary
Day 29 ± 2 days	AE query, medical/medication update

4-Week Follow-Up	Symptom questionnaires,
	Eye evaluations (Efficacy /Safety)
	Dispensation of study drug and subject diary

\downarrow

	Collection and review of study drug/diary
Visit 4	AE query, medical/medication update
Day 57 ± 2 days	Symptom questionnaires
8-Week Follow-Up	Eye evaluations (Efficacy /Safety)
	Dispensation of study drug and subject diary

↓

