4.4 Justification of Study Design

Based on CYS-002 results Novaliq plans a confirmatory study in DED patients having

(NEI grading) at baseline. This population responded best in signs and

symptoms.

The study will be a randomized, double-masked, vehicle controlled study to demonstrate efficacy and safety of CyclASol after 1-month treatment duration. Vehicle controlled studies are currently the standard for DED studies. Randomization and double masking are state of the art measures to reduce bias. Fast onset of efficacy is important for patients and their compliance to therapies, thus early demonstration of efficacy (e.g. at 1 month) is desired and highly clinically relevant. Moreover, DED is a fluctuating condition with phase-like recurring dry eye complaints that may be linked to seasonal and / or environmental changes (van Setten, *et al.* 2016), thus a primary endpoint assessment at a shorter treatment duration is considered clinically relevant and has a greater potential to capture the true drug effect.

Total corneal fluorescein staining (NEI grading) and total OSDI have been selected as the primary sign endpoint and primary symptom endpoint, respectively. The two primary endpoints will be tested in a sequential order with total corneal fluorescein staining being tested first. Both primary endpoints are well accepted by regulators and clinicians. The hierarchical testing has been selected to protect the α – error. Corneal staining is being tested first as the CYS-002 data for this endpoint is stronger.

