5.3 Inclusion Criteria

Each subject must:

- a. Be at least 18 years of age;
- b. Provide written informed consent;
- c. Have a subject reported history of Dry Eye Disease
- d. Be currently using (within 30 days before Visit 0) over-the-counter (OTC) eye drops, lubricating gels and/or artificial tears for dry eye symptoms at Visit 0;
- e. Have an OSDI score of at Visit 0 and Visit 1;
- f. Have a total corneal fluorescein staining score of
- g. Have a total lissamine green conjunctival score (sum of temporal and nasal regions) of
- h. Have an unanesthetized Schirmer's Test score
- j. Be able and willing to follow instructions and participate in all study assessments and visits.

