8.3 Examination Procedures

8.3.1 Procedures to be Performed at Each Study Visit with Regard to Study Objective(s)

The procedures outlined in this section will performed as described in Appendix 2.

Visit 0 (Day -14 ± 2 days): Screening

- Informed consent / HIPAA
- Medical/medication history and demographic data
- Urine pregnancy test for females of childbearing potential
- Ocular Surface Disease Index (OSDI)
- Visual acuity (ETDRS)
- Slit-lamp biomicroscopy
- Fluorescein staining (NEI scale)
- Intraocular pressure
- Dilated fundoscopy
- Review of qualification criteria
- In-office instillation of run-in drops to qualified subjects
- Dispensation of subject diary and run-in for bilateral, BID dosing until Visit 1 as described in Section 7.1.3
- Adverse event query

[figure not shown]
• Qualified subjects are scheduled for Visit 1

Visit 1 (Day 1): Baseline / Randomization

- Collection and review of run-in and diary
 - Calculate subject compliance as described in Section 8.5
 - Ask subject if he/she dosed with run-in the morning of Visit 1 and, if applicable, record the time of the dose
- Medical/medication history update
- Adverse event query

٠	OSDI
٠	
•	Visual acuity Slit lamp biomicroscopy
i	Slit-lamp biomicroscopy
•	Fluorescein staining (NEI scale)
	Review of qualification criteria
•	Randomization
•	In-office instillation of randomized study drug
•	Dispensation of subject diary and randomized study drug for bilateral,
-	BID dosing until Visit 2 as described in Section 7.1.3
•	Adverse event query Randomized subjects are scheduled for Visit 2
Viait 1	
VISIU Z	(Day 15 ± 1): 2-Week Follow-Up
•	Collection and review of study drug and subject diary

[figure not shown]
- Medical/medication history update
- Adverse event query

[figure not shown]

- Adverse event query
- Schedule for Visit 4

Visit 4 (Day 57 ± 2): 8-Week Follow-Up

• Collection and review of study drug and subject diary

8.3.2 Early Termination/Discontinuations

If a subject is discontinued from the study before Visit 5 (Day 85 ± 2 days), then all safety evaluations that are to be performed at Visit 5 should be performed and the demographic data should be obtained on the day of early termination/discontinuation or at the discretion of the investigator.

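### The primary ANCOVA could also adjust for the Visit 0 score, already scheduled before randomization: an optional precision gain of unknown, possibly nil, size, not an error

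*Combined protocol and SAP*

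**What the plan says.** Section 10.4.5 (and the synopsis) analyses each primary endpoint with an "ANCOVA model with terms for baseline value, treatment, and the interaction of treatment by baseline value"; the interaction is retained only if its p-value is below 0.10. Section 10.4.1 fixes which value that is: "Baseline is defined as the last non-missing measure prior to administration of study drug". For a randomized subject this is normally Visit 1.

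An earlier score of each measure is also scheduled. Section 8.3.1 lists OSDI and NEI fluorescein staining under both Visit 0 and Visit 1. The OSDI entry criterion in section 5.3 reads "Have an OSDI score of at Visit 0 and Visit 1", with the threshold blacked out. The visit wording of the staining criterion is also blacked out. Between the two visits, section 4.1 states: "During the run-in period, subjects will dose Systane Balance bilaterally BID for approximately two weeks".

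None of the sensitivity models visible in 10.4.5 uses Visit 0. The t-tests and Wilcoxon tests carry no covariate, and the repeated-measures model lists treatment, visit, their interaction and a subject effect.

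Section 10.3 plans 142 subjects per arm: 90% power for staining (difference -0.85, SD 2.2) and 82% for OSDI (difference -5.0, SD 14.5), two-sided alpha 0.05.

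**The concern.** A second pre-randomization measurement of the same outcome can carry information on a subject's underlying severity that one measurement misses. If it does, leaving it out keeps explainable variation in the residual, with wider confidence intervals and less power than the collected data allow. Because Visit 0 precedes randomization, adjusting for it cannot bias the treatment contrast. In a trial of this size it cannot cost precision beyond one degree of freedom.

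OSDI has the most to gain. It is second in the fixed sequence and has the lower planned power, so a claim on both sign and symptom has less margin there.

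**Working it through.** **1. The plan's own power.** Two-sample comparison, n = 142 per arm, two-sided alpha 0.05, inputs from section 10.3. The noncentrality is difference / (SD × √(2/n)).
- Staining: 0.85 / (2.2 × √(2/142)) = 0.85 / 0.2611 = 3.26. Power is 90.1% (noncentral t) or 90.2% (normal approximation), against 90% stated.
- OSDI: 5.0 / (14.5 × √(2/142)) = 5.0 / 1.7208 = 2.91. Power is 82.5% or 82.8%, against 82% stated.
- Enrolment: 142 / 0.9 = 157.8, so 158 per arm and 316 in total, as stated.

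All three reproduce with no Visit 0 term.

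**2. What Visit 0 can add.** Let r01, r0y and r1y be the correlations of Visit 0 with Visit 1, Visit 0 with Day 29, and Visit 1 with Day 29. All values below are assumptions; the documents give none.

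Residual variance ratio, two baselines to one = (1 − R²) / (1 − r1y²), with R² = (r0y² + r1y² − 2·r0y·r1y·r01) / (1 − r01²).

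- Equal correlation ρ: the reduction is ρ² / (1 + ρ)². At ρ = 0.3, 0.09/1.69 = 5.3%; at 0.5, 0.25/2.25 = 11.1%; at 0.7, 0.49/2.89 = 17.0%.
- Some decay (r01 = r1y = 0.5, r0y = 0.4): R² = (0.16 + 0.25 − 0.20)/0.75 = 0.28; the ratio is 0.72/0.75 = 0.96, a 4.0% reduction.
- AR(1)-like decay (r0y = r01 × r1y): R² = r1y², so the reduction is 0%.

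**3. Effect of entry selection.** Three normal scores were simulated, keeping only subjects above a cut at both Visit 0 and Visit 1. The real cut-offs are blacked out, so cuts at the mean and at the mean + 0.5 SD are assumed. Reduction in residual variance among those kept:

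| Correlation before selection | Equal at all visits | Visit 0 correlates 15% less with Day 29 |
|---|---|---|
| 0.3 | about 2% | about 1-1.5% |
| 0.5 | 5-6% | 2-3% |
| 0.7 | 9-11% | 2-3% |
| 0.8 | 13-14% | just under 1% |

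At ρ = 0.5, selection at the mean cuts the gain from 11.1% to about 6%. Under AR(1)-like decay it stays at zero.

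**4. Translation to power.** If 2.2 and 14.5 are residual SDs of the one-baseline model, scale them by √(1 − reduction) (noncentral t, n = 142 per arm):

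| Reduction | Staining | OSDI alone |
|---|---|---|
| 0% | 90.1% | 82.5% |
| 1% | 90.3% | 82.9% |
| 3% | 90.9% | 83.7% |
| 5% | 91.4% | 84.4% |
| 10% | 92.8% | 86.3% |
| 14% | 93.8% | 87.8% |

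**5. The other reading of the SDs.** Section 10.3 does not say whether 2.2 and 14.5 are covariate-adjusted. If they are raw SDs of change, then under equal correlation without selection the one-baseline ANCOVA has residual SD = SD × √((1 + ρ)/2). For ρ from 0.3 to 0.7 it already reaches about 94-98% for staining and 88-95% for OSDI. Visit 0 then adds about 0.5-3 and 1-5 points.

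**The case against.** The strongest reply is that nothing is wrong. ANCOVA on a single baseline is valid, and the planned power is met without Visit 0. That stands, and is why this is offered only as an improvement.

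The second reply is that the size is unknown and may be nil. Visit 0 is the older score. It is taken before the run-in, in subjects using assorted over-the-counter products, while Visit 1 follows about two weeks of common dosing and lies closer to Day 29. The 15%-lower scenario is therefore at least as plausible as equal correlation, and no passage supports correlations of 0.7-0.8. This also stands.

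A reader might go further and infer that precision is lost because section 4.4 says "DED is a fluctuating condition with phase-like recurring dry eye complaints", or because the synopsis says "A 14-day study-run-in period will be used for subject selection before randomization". The documents do not support either inference. Section 4.4 uses fluctuation to justify an early endpoint and links it to season and environment. Lower visit-to-visit correlation shrinks the gain, since ρ²/(1 + ρ)² falls with ρ, and slow drift makes the older score less informative. Selection at both visits narrows the range and also reduces the gain.

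Finally, the strata, sections 10.4.6-10.4.7 and the content of 10.5 are not visible, so an adjusted analysis there cannot be excluded. The primary model text is visible, and it has one baseline term.

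What none of this removes is the asymmetry: the possible gain is real, and the cost is one degree of freedom.

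**Conclusion.** The point holds as an optional, nearly costless efficiency gain. The trial schedules two pre-randomization scores for each primary endpoint, and the primary model uses one. Residual variance may fall by anything from 0% to about 14% over the assumed range with selection, with 1-3% a reasonable cautious expectation. On the residual-SD reading, 1-3% is worth 0.3-0.8 points of power for staining and 0.4-1.1 for OSDI; 5% is worth about 1.4 and 1.9. These figures rest on assumed correlations, normal scores and assumed entry cut-offs.

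The documents do not support saying that the plan is in error, that it falls short of its stated power, or that precision is certainly lost.

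**What to change.** In section 10.4.5 and the matching synopsis text, prespecify before unmasking:
- The Visit 0 score of the same measure (study eye for staining, subject for OSDI) is added as a second continuous covariate in each primary ANCOVA, as a main effect only.
- Visit 1 remains the baseline for calculating change, for the treatment-by-baseline interaction step and for the percentile contrasts. With no interaction of its own, Visit 0 does not alter how those contrasts are formed.
- The rule for a subject whose Visit 1 value is missing, where section 10.4.1 would make Visit 0 the baseline, is written down.
- The imputation models in section 10.4.3 include the Visit 0 score.

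It would help to state the between-visit correlations, from the sponsor's phase 2 study if it has two pre-treatment scores, or from masked pooled data.

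Cost: a few sentences, one model term and one degree of freedom per primary model. No new data are needed, and the endpoints, the treatment contrast and the testing order are unchanged. Adding the term after unmasking would look selective, so the timing matters.

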The primary comparisons in this study will be between CyclASol versus vehicle at Day 29. The primary efficacy endpoints (e.g. change from baseline in corneal fluorescein staining [total NEI] and OSDI) will be analyzed separately using an ANCOVA model with terms for baseline value, treatment, and the interaction of treatment by baseline value (the interaction term will be maintained in the model only if the p-value for the term is <0.10).

Least squares mean for each treatment group and for the difference between treatment groups will be presented from the model together with two-sided p-values and 95% confidence intervals. In the event that the interaction of treatment by baseline value is significant, estimate and contrast statements will be used to determine the treatment group means and differences at the 25th, 50th, and 75th percentile of the baseline score over treatment groups.

Two-sample t-tests, Wilcoxon rank sum tests and mixed-effect repeated measures analysis comparing treatment groups will be performed as sensitivity analyses.

The primary analysis will use the Full Analysis Set (FAS) with available data per subject. Additional robustness analyses will include repeating the primary analysis on the per protocol set (PPS); the FAS imputing missing data using last observation carried forward (LOCF); the FAS imputing missing data using Markov Chain Monte Carlo (MCMC) multiple imputation methodology under different assumptions of missingness (at random and not at random); and an analysis of trimmed means (Permutt et al., 2017).

Safety Variables

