6.1.4 Criteria for Effectiveness

Hierarchical fixed sequence testing will be employed to maintain the type I error rate. The primary analyses will first test the difference in the mean change from baseline corneal fluorescein staining (NEI scale) total score between treatments at Day 29. If the test of the difference is statistically significant at the two-sided alpha = 0.05 level in favor of CyclASol, then the study will be considered a success; CyclASol will be declared to be superior to vehicle in the mean change from baseline corneal fluorescein staining (NEI scale) total score at Day 29; and the difference in the mean change from baseline total OSDI score between treatments at Day 29 will be tested at the two-sided alpha = 0.05 level.

If in addition to a statistically significant test of the difference in the mean change from baseline corneal fluorescein staining (NEI scale) total score at Day 29 in favor of CyclASol, the test of the difference in the mean change from baseline total OSDI score at Day 29 is also statistically significant in favor of CyclASol, then CyclASol will be declared to be superior to vehicle in both the mean change from baseline corneal fluorescein staining (NEI scale) total score and the mean change from baseline total OSDI score at Day 29.

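### Does keeping the treatment-by-baseline interaction at p<0.10 leave the primary test undefined?

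*Combined protocol and SAP*

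**What the plan says.** Section 10.4.5 (and the matching synopsis paragraph) analyses Day 29 change in corneal staining and in OSDI by separate ANCOVAs with baseline, treatment and their product, with the proviso that "the interaction term will be maintained in the model only if the p-value for the term is <0.10". Least-squares means are reported by arm, and those "for the difference between treatment groups will be presented from the model together with two-sided p-values and 95% confidence intervals". If the interaction is significant, "estimate and contrast statements will be used to determine the treatment group means and differences at the 25th, 50th, and 75th percentile" of baseline.

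Section 10.2 states H01 and H02 each as one difference in mean change at Day 29. Sections 6.1.4, 10.2 and 10.4.4 let the study succeed, and OSDI be tested, on one condition: "If the test of the difference is statistically significant at the two-sided alpha = 0.05 level in favor of CyclASol".

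Section 10.3 sizes the staining comparison "assuming a true difference (CyclASol minus vehicle) of -0.85, a common standard deviation of 2.2", and says that "One-hundred forty-two (142) ITT subjects (study eyes) per treatment group yields 90% power to reject" H01. For OSDI it assumes -5.0 with SD 14.5 and claims 82%.

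Sections 10.4.6 and 10.4.7, the content of 10.5 and a figure after 10.4.4 are not visible in the public text.

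**The concern.** Two things look wrong. First, a preliminary test on outcome data selects the confirmatory model, a practice that can distort the error rate of the later test.

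Second, once the interaction is in the model, the treatment difference is no longer one number, because it varies with the baseline at which it is evaluated. The visible text gives no evaluation point for the least-squares means and does not call the percentile differences descriptive. A reader could imagine success being claimed at whichever percentile is significant, or being withheld unless all three are.

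The staining test decides both study success and access to OSDI. At the planned staining effect, with no true interaction, the three percentile contrasts disagree on significance in 5.1–8.3% of all simulated trials. A choice made after unmasking could therefore matter.

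**Working it through.** **1. The plan's own figures.** Standard error = SD × √(2/n).
- Staining: 2.2 × √(2/142) = 0.261; 0.85/0.261 = 3.256; power ≈ Φ(3.256 − 1.960) = 0.902 (noncentral t: 0.901).
- OSDI: 14.5 × √(2/142) = 1.721; 5.0/1.721 = 2.906; power ≈ Φ(0.946) = 0.828 (noncentral t: 0.825).
- Enrolment: 284/0.90 = 315.6, so 316.

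The stated 90%, 82% and 316 are reproduced.

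**2. Which difference the text tests.** Set side by side: 10.2 has one difference per hypothesis; 6.1.4, 10.2 and 10.4.4 have one test per endpoint; 10.4.5 attaches p-values and intervals to the least-squares mean difference. The percentile sentence mentions means and differences, with no p-value, alpha or success rule. A difference at a given percentile is conditional on baseline and is not the quantity in H01. Least-squares means are by usual convention evaluated at the overall mean of the covariate.

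**3. Why the preliminary test does no harm there.** With separate slopes b1 and b0, arm means of baseline x̄1 and x̄0, and within-arm sums of squares S1 and S0, let d(x0) be the treatment difference at baseline x0. Then

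Cov(d(x0), b1 − b0) = −σ²[(x̄1 − x0)/S1 + (x̄0 − x0)/S0].

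With equal arms and x0 at the overall mean, x̄0 − x0 = −(x̄1 − x0). The covariance becomes −σ²(x̄1 − x0)(1/S1 − 1/S0), a product of two small chance imbalances. The deciding difference is nearly uncorrelated with the interaction estimate, so selecting on the interaction barely disturbs it.

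**4. Simulation, no true interaction.** Inputs from 10.3: 142 per arm and the planned effects and SDs. Assumed, because the documents do not give them: baseline-to-change correlation 0, −0.3 or −0.5; baseline normal, flat or right-skewed for staining, and normal or right-skewed for OSDI. The term is kept in about 10% of trials per endpoint. Power is at correlation 0; H02 power ignores the gate.

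| What decides if the term is kept | Two-sided error, staining | Two-sided error, OSDI | H01 power | H02 power |
|---|---|---|---|---|
| Interaction never fitted | 4.89–5.16% | 4.96–5.03% | 89.5–90.3% | 82.4–82.8% |
| Difference at overall mean baseline | 4.92–5.17% | 4.97–5.04% | 89.5–90.3% | 82.4–82.8% |
| Median baseline only | 5.00–5.89% | 5.01–5.21% | – | – |
| Any of the three percentiles | 7.93–9.08% | 7.68–8.01% | – | – |
| All three percentiles | 4.45–4.68% | 4.48–4.55% | 82.7–84.2% | 76.3–77.1% |

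Success counts only in favor of CyclASol (nominal 2.5%). In that direction the any-percentile rule gives 3.96–4.57% for staining and 3.89–4.02% for OSDI.

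**5. Where the bad figures arise.** A second set of runs (normal staining baseline, mean 11.5, SD 1.5, correlation 0) splits the result by whether the term was kept.
- Null, favorable direction: kept in 9.78% of trials. Among those, the mean-baseline difference is significant in 2.81% and at least one percentile in 17.77%. Extra error = 0.0978 × (0.1777 − 0.0281) = 0.0146; 0.0243 + 0.0146 = 0.039.
- At −0.85: kept in 9.73%. Among those, the mean-baseline difference is significant in 91.06% and all three percentiles in 31.45%. Loss = 0.0973 × (0.9106 − 0.3145) = 0.058; 0.897 − 0.058 = 0.839.

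The whole excess or loss comes from replacing the least-squares difference with a percentile rule. None comes from the p<0.10 step.

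**6. With a true interaction.** Assuming −0.3 per baseline point in the second set, the term is kept in 53% of trials. Power is 89.6% at the mean baseline and 89.3% for the model without interaction. In further runs the two approaches gave a different success decision in at most 0.02% of trials without an interaction and in 0.2–0.3% with this one.

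**The case for a change.** The strongest reply is that a test which gates a second primary endpoint should not rest on a software convention. The percentile differences sit within the primary analysis section, apart from the analyses labelled as sensitivity. An interaction is also not far-fetched: section 4.4 says that the population chosen by baseline staining responded best. Under the assumed −0.3 per point, power for staining is 94% if any percentile counts and 55% if all must agree, so the reading would matter a good deal.

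A further trap is the raw treatment coefficient from the interaction model, which is the difference at baseline zero. Used as the test, it gives 4.6–4.7% error in the favorable direction.

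What stands is that the evaluation point is not written down in the visible text, and neither is a sentence calling the percentile differences descriptive. What does not stand is the step from there to a defect. The any-percentile rule would give three chances at a hypothesis that the plan tests once, within a scheme adopted to hold the type I error. The all-percentiles rule appears nowhere. The raw coefficient is ruled out because the plan asks for least-squares means. Since part of the statistical section is not visible, silence in the public text is also weak evidence that nothing was specified.

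**Conclusion.** No change follows. The plan leaves a detail that an analyst fills in the standard way: the least-squares mean difference, taken at the overall mean baseline, tests H01 and then H02, and the percentile differences describe any interaction. Under that reading, two-sided error is 4.9–5.2% for staining and about 5.0% for OSDI, and the planned power is kept. Removing the interaction term would alter power by no more than 0.1 point without a true interaction, and by about 0.2 point (89.6% against 89.3% after rounding) with one of −0.3 per point.

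The larger figures depend on decision rules that the visible text does not contain, and only 4.0–4.6% against 2.5% for staining would be false success. The results rest on assumed baseline distributions and correlations. The near-zero covariance in step 3 explains why the mean-baseline result hardly depends on them. The any-percentile figure does move with the shape, reaching 9.7–10.0% two-sided for an extreme bimodal staining baseline, but that rule is not the plan's.
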